1. RESEARCH QUESTIONS

1.1. OVERVIEW OF RESEARCH QUESTIONS

Research questions in this study are framed by a descriptive evaluation design that will be used to measure changes in participant outcomes after participation in the Fatherhood Works Program. Analyses will measure the differences in primary and secondary outcomes from orientation to one year after program enrollment. Primary outcomes refer here to changes in parenting and co-parenting *behaviors*. Secondary outcomes refer here to the *attitudes* that theoretically facilitate and reflect behaviors. Implementation analyses seek to demonstrate whether or not participants are receiving the intended amounts of FWP services.

No	Research Question	Implementation or Outcome?
I1	To what extent is the Nurturing Fathers curriculum offered to and received by program participants?	Implementation
I2	To what extent are additional primary workshops offered to and received by program participants?	Implementation
I3	To what extent did the CQI team carry out the steps in the CQI plan each program year?	Implementation
R1	How did parenting behavior measures change from program enrollment to 1 year after enrollment?	Primary Outcome
R2	How did parenting attitude measures change from program enrollment to immediately following program completion?	Secondary Outcome
R3	How did co-parenting behavior measures change from program enrollment to 1 year after enrollment?	Primary Outcome
R4	How did employment attitude measures change from program enrollment to 1 year after enrollment?	Secondary Outcome

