3. LOGIC MODEL

Clearly demonstrate how the research question(s) (and the related implementation features and/or participant outcomes) link to the proposed logic model and the theory of change for the program. You may append a copy of your logic model to this document.

The appended logic model specifies a theory of change for delivering virtual and in-person primary services and standard support services as part of the Fatherhood Works Program. Service delivery processes specified in the model are linked to the desired outcomes for healthy family relationships. Model specification incorporates a descriptive study design to measure change in primary and secondary participant outcomes from program enrollment to one year after enrollment.

Service delivery processes: Key aspects of service delivery processes in the theory of change—goals, inputs, activities, and outputs—articulate the experiences that are designed to solve specific problems for those who agree to participate in the Fatherhood Works Program. Solving each problem identifies three broad service delivery goals to maximize participation benefits for study groups as explained below:

- **Goal 1 – Deliver primary curricula workshops to Fatherhood Works Program participants:** Project participants will be offered three primary curricula through Goodwill of Central Texas and their facilitation partner Any Baby Can, in combination with support services and case management. The Nurturing Fathers curriculum will help to develop participants' skills and healthy attitudes to engage in healthy parenting and co-parenting behaviors. The Creating a Safe Home seminar will help to build participant knowledge about domestic violence and child neglect to reduce these behaviors. The Workforce Advancement workshop will help to develop participants' job search skills and increase to the likelihood of securing stable, gainful employment. Participant engagement in the primary curricula and local evaluation surveys will take place after receiving the FWP orientation and providing project staff with informed consent to participate in study activities.

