- **Goal 2 – Deliver support services to Fatherhood Works Program participants:** Project participants will be offered support services, including case management, transportation supports, and referrals to additional services within and external to Goodwill. These support services are intended to increase the likelihood that participants will benefit from primary services and to reduce barriers to program retention.
- **Goal 3 - Conduct Continuous Quality Improvement (CQI) efforts to ensure full implementation of program services:** Reports prepared and presented to the CQI Team by evaluators in the CQI process will use a series of performance indicators to track key outputs over time to identify any *primary or support FWP services* delivered to study groups that might fall short of the intended amounts to be offered (i.e., fidelity standards) and received (i.e., dosage thresholds) by them. The CQI Team will then work with project staff to develop and implement performance interventions to address any outputs that need improvement to ensure the services offered to, and received by, participants meet the intended amounts by the end of each program year.

Desired Outcomes: Outcomes specified in the logic model theorize the primary and secondary outcomes that are desired for program participants after they receive primary and support services. Secondary outcomes are the improved attitudes that facilitate and reflect participant engagement in healthy parenting and employment behaviors. Primary outcomes are the healthier parenting and co-parenting behaviors exhibited by participants that ultimately define the benefits of Fatherhood Works Program participation.

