The main goal of this descriptive study is to assess pre-post change scores in the attitudinal outcomes listed above among program participants before (pre) and immediately following program completion, and in the behavioral outcomes listed above among program participants before and 1 year after enrolling in primary workshops. We will use paired sample t-tests to assess the magnitude and significance of changes among program participants in the analytic sample for each outcome. We will adjust our p-values for multiple hypothesis testing and report the adjusted p-values in the appendix of the final report.

For the implementation analysis, program fidelity will be descriptively reported by the percentage of enrolled participants who receive: 1) any primary workshops, 2) employment supports, 3) substantive service contacts, 4) referrals. The program aims to provide all participants each of these four program components, so the percentage of participants who receive each of these will be compared to the 100% benchmark. Number of substantive service contacts per participant will also be compared to the benchmark of 8 SSCs set by OFA for FIRE grantees.

Dosage will be measured by percent of target primary workshops participants attend on average (using 90% as a benchmark), and categories of attendance (initial, halfway, 90%, 100%) will be reported and compared to targets established by the program and reported on page 3 above. Exploratory analysis will examine how dosage varies by workshop characteristics (e.g., virtual vs in-person) and participant characteristics (e.g., age, employment status, relationship status).

2. Data Archiving and Transfer

Briefly describe the planned approach data arching and transfer by addressing questions below.

What procedures and parameters are established for all aspects of data/information collection necessary to support archiving data collected as part of the evaluation?

Examples include informed consent, data maintenance, de-identifying data procedures.

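### The SAP's implementation measures pool the three curricula and count only receipt, so as written they do not answer I1 or I2, and no analysis is stated for I3

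*SAP*

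**What the plan says.** Protocol section 1.1 poses three implementation questions. I1 asks how far the Nurturing Fathers "curriculum offered to and received by program participants" is delivered. I2 asks: "To what extent are additional primary workshops offered to and received by program participants". I3 asks: "To what extent did the CQI team carry out the steps in the CQI plan each program year".

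The Logic Model (Evaluation Plan section 3) states under Goal 1: "Project participants will be offered three primary curricula". These are Nurturing Fathers, Creating a Safe Home and Workforce Advancement. Goal 3 of the same section says CQI reports will identify services that may miss the "intended amounts to be offered (i.e., fidelity standards) and received (i.e., dosage thresholds) by them". There, fidelity belongs to what is offered and dosage to what is received.

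The implementation paragraph of the SAP (section 1, Analytic approach) says "program fidelity will be descriptively reported by the percentage of enrolled participants who receive" each of four components: any primary workshop, employment supports, substantive service contacts and referrals. Each is compared with 100%. Dosage is the "percent of target primary workshops participants attend on average", compared with 90%. Attendance categories (initial, halfway, 90%, 100%) are compared with program targets. An exploratory analysis looks at dosage by workshop and participant characteristics, with virtual versus in-person delivery as the workshop example. Under Handling missing data, undocumented attendance is taken to mean that the service was not received.

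**The concern.** The questions and the measures do not line up. I1 and I2 divide the primary services by curriculum; the SAP combines them. I1 and I2 each have an offered half and a received half; the SAP measures only the received half, and it calls part of that fidelity, the word the protocol attaches to amounts offered. I3 is posed and then not taken up.

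Followed as written, the analysis would report that most men received some primary workshop without showing whether the main parenting course reached them. It would also not separate a course that was never run from one that was run but not attended, because both appear as absent attendance records. These are different failures with different remedies. The Background section of the protocol rests the rationale for R1 to R4 on Nurturing Fathers, so its delivery and uptake are what a reader would want beside those results.

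**Working it through.** The SAP gives no implementation figure to reproduce. The check sets each question against the stated measures and then bounds what the pooled measures can hide.

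**Questions against measures**

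| Question | What it needs | What the SAP states |
|---|---|---|
| I1, offered | Nurturing Fathers offered against planned | None |
| I1, received | Nurturing Fathers receipt and dose | Pooled receipt and pooled dosage only |
| I2, offered | Other workshops offered against planned | None |
| I2, received | Receipt and dose for the other workshops | Pooled receipt and pooled dosage only |
| I3 | CQI steps carried out, by program year | None |

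**Bound on the primary-workshop component.** Let A be the percentage receiving at least one primary workshop, N the percentage receiving Nurturing Fathers, and O the percentage receiving one of the other two. Because A counts anyone in either group:

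- N ≤ A and O ≤ A
- N + O ≥ A

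So N can lie anywhere from 0 to A, and so can O. With A = 100% for illustration, the benchmark is met whether N is 0% or 100%.

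**Bound on pooled dosage.** Let w be the Nurturing Fathers share of total target hours, with the same targets for every man. The documents do not give w, so the values below are assumptions. Pooled mean dosage is

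D = w × d_N + (1 − w) × d_O

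where d_N and d_O are mean attendance at Nurturing Fathers and at the other workshops. Set D = 0.90 and let one part be fully attended:

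- Lowest d_N = 1 − 0.10/w
- Lowest d_O = 1 − 0.10/(1 − w)

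| Assumed w | Lowest d_N | Lowest d_O |
|---|---|---|
| 1/3 | 1 − 0.10/0.333 = 70% | 1 − 0.10/0.667 = 85% |
| 0.8 | 1 − 0.10/0.8 = 87.5% | 1 − 0.10/0.2 = 50% |

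A larger w protects the Nurturing Fathers figure and exposes the others; a smaller w does the reverse. The benchmark therefore limits what can be hidden but does not supply the separate answers that I1 and I2 ask for.

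**Does the exploratory breakdown supply them?** It covers dosage only and does not name curriculum. Delivery mode is no substitute: the Program Summary has Nurturing Fathers offered both virtually and in person and Creating a Safe Home offered virtually, so a comparison by mode mixes mode with curriculum.

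**The case against.** The strongest reply has four parts.

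- **The outcome questions treat the primary services as one package.** Protocol section 1.2 defines the intervention for R1 to R4 as all three services, and the Background describes Nurturing Fathers in combination with other programming. Pooled dose is therefore relevant to the intervention under evaluation. This stands, and the pooled figures should stay. It does not answer I1 and I2, which the protocol poses separately.
- **The dosage benchmark would catch gross non-delivery.** A man who attends everything except Nurturing Fathers scores 1 − w. With three equally weighted curricula that is 2/3, or 67%, which misses 90%; he would reach 90% only if w were 0.10 or less. This also stands. The masking that remains is the partial kind bounded above.
- **Amounts offered and CQI activity are tracked elsewhere.** Goal 3 of the Logic Model describes CQI indicators for offered and received amounts, and Evaluation Enrollment lists nFORM metrics, site visit findings and CQI process findings as implementation data. This supports feasibility, but the SAP carries none of it into a stated analysis.
- **Part of the dosage plan could not be seen.** The attendance targets are said to be on a page that was not available for review, and they may be set by curriculum. That absence is not counted as a fault. The SAP text still states no reporting by curriculum and no measure of what was offered.

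Two stronger readings should be resisted. A reader might infer that a man who attends only the domestic violence seminar counts as full fidelity. He would count on one component of four, each judged separately, and the SAP defines no person-level fidelity status. A reader might also infer that I1 and I2 cannot be answered at all. The documents show only that the specified analysis does not answer them; the underlying records may allow it.

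**Conclusion.** The point holds as a mismatch between the stated measures and the plan's own questions. I1 and I2 get no separate estimate of receipt or dose, their offered halves have no measure, fidelity is used in a sense contrary to the Logic Model, and I3 has no stated analysis.

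The bound on the primary-workshop percentage (0% to A%) is pure logic and needs no assumption. The dosage bounds depend on the assumed hour share w and on common targets, so they show a possible size and do not predict one. These are descriptive implementation results: no outcome estimate, test or sample size changes. The change should be made because I1 to I3 are questions the protocol commits to, and because change in the outcomes is hard to interpret without the delivery and dose of the course on which their rationale rests.

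**What to change.** In the implementation paragraph of the SAP:

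1. Report the percentage receiving, the percentage of target hours attended and the four attendance categories separately for Nurturing Fathers (I1) and for Creating a Safe Home and Workforce Advancement (I2). Keep the pooled figures beside them.
2. Relabel the present percentage-receiving measures as receipt, and reserve fidelity for amounts offered, as in the Logic Model.
3. Report sessions or hours offered against planned, by curriculum, from the CQI output indicators or from nFORM session records if these hold them.
4. For I3, tabulate CQI plan steps completed over steps planned, by program year, from the CQI process findings.

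The cost is more table rows. The Nurturing Fathers figure may be less favorable than the pooled one. Evaluation Enrollment names workshop hours received as an nFORM metric, but nothing in the documents shows that nFORM holds hours offered, so the evaluator must confirm that source before committing to item 3. No new data from participants are needed.
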